## 3.0 Sample Size:

Up to 30 individuals with PPA and their communication partners (spouse, family member, or close friend) will be enrolled. A formal sample size estimate and power analysis was not completed as this is a feasibility study to examine the added benefit of extended multi-component treatment for persons with PPA. Data from this Phase I expansion of our current Phase II trial will be used to establish feasibility of the protocol, to make protocol adjustments, and to collect preliminary effectiveness data for an upcoming grant submission.

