## 19.0 Data Monitoring Plan to Ensure the Safety of Participants:

An adverse event (AE) is any untoward medical occurrence in a participant during participation in the clinical study that is attributed to the cognitive testing or the engagement in the online therapy intervention. An adverse finding can include a sign, symptom, abnormal assessment, or any combination of these. While all adverse events will be reported, some may be expected due to the participant's medical condition. Each adverse event will be classified as being attributable or not to participation in the study. A serious adverse event (SAE) is any AE that results in one or more of the following outcomes that are attributable to participation in the study:

- · Death
- · A life-threatening event
- · Inpatient hospitalization or prolongation of existing hospitalization
- An important medical event based upon appropriate medical judgment

Grading Scale: AEs will be labeled according to severity, which is based on their impact on the participant. An AE will be termed "mild" if it does not have a major impact on the participant, "moderate" if it causes the participant some minor inconvenience, and "severe" if it causes a substantial disruption to the participant's well-being.

Study Relatedness Criteria: AEs will be categorized according to the likelihood that they are related to the study intervention. Specifically, they will be labeled definitely unrelated, definitely related, possibly related, or probably related to the study intervention.

Reporting and Follow Up: AEs will be reported by severity, relatedness to the intervention, action taken and outcome. Each adverse event will be reported separately. All AE reports and annual summaries will be de-identified and will not include participant-identifiable material. The PI will engage in continuous close monitoring of research participants with reporting of AEs to the Northwestern University Institutional Review Board.

SAEs that are unanticipated, serious, and possibly related to the study intervention will be reported to Northwestern University's IRB within 24 hours of notification of its occurrence.

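### The mild and moderate adverse-event grades are not mutually exclusive as worded, so the choice between them is left to the grader

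*Protocol*

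**What the plan says.** The protocol, Section 19.0 (Data Monitoring Plan), puts severity on a single axis: "AEs will be labeled according to severity, which is based on their impact on the participant". It then defines three grades in one sentence:

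- mild: "if it does not have a major impact on the participant"
- moderate: "if it causes the participant some minor inconvenience"
- severe: "if it causes a substantial disruption to the participant's well-being"

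The same section gives the use of the grade: "AEs will be reported by severity, relatedness to the intervention, action taken and outcome". It also mentions annual summaries and reporting to the IRB.

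Seriousness is defined separately, by outcome and attribution: "A serious adverse event (SAE) is any AE that results in one or more of the following outcomes". The 24-hour report to the IRB applies to events that are unanticipated, serious and possibly related.

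**The concern.** An ordered severity scale needs each event to have one grade, and a worse event never to rank below a lesser one. Here mild has an upper limit only (anything short of a major impact), and moderate is described by a small impact that lies inside that limit. As worded, moderate is a subset of the grade meant to sit below it.

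At stake is the meaning of the mild and moderate labels in the adverse-event reports. If the text does not fix the label, it partly reflects the grader. Section 17.0 lists fatigue or frustration with the online intervention among the potential adverse events, and an episode that causes a minor inconvenience fits both grades. Section 3.0 says the data will serve to establish feasibility, adjust the protocol and support a grant submission, so a description of tolerability by grade could be carried forward.

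**Working it through.** No figure in the plan is involved and no formula applies. The check places the three definitions on the protocol's own axis and asks which grades each level of impact meets. All inputs come from Section 19.0.

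Two assumptions about plain meaning are used. A minor inconvenience is not a major impact. A substantial disruption to well-being is a major impact. The protocol does not say whether the converse holds, that is, whether every major impact is also a substantial disruption. Level 4 below exists only if it does not.

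| Level of impact | Meets mild? | Meets moderate? | Meets severe? |
|---|---|---|---|
| 1. No inconvenience | yes | no | no |
| 2. Minor inconvenience | yes | yes | no |
| 3. More than minor inconvenience, short of a major impact | yes | no | no |
| 4. Major impact, short of substantial disruption (if the two differ) | no | no | no |
| 5. Substantial disruption | no | no | yes |

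Three results follow.

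1. **Overlap.** At level 2 both mild and moderate apply. Nothing in the protocol says which to use: there is no rule to take the highest grade, no statement that moderate excludes mild, no worked example and no reference to an external scale.
2. **Order.** At level 3 only the mild wording applies, although the event is worse than one at level 2 that may be called moderate.
3. **Possible gap.** At level 4, if it exists, no grade applies.

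Next, test the simplest repair, a rule to assign the highest grade that applies. Level 2 becomes moderate, so the overlap goes. Level 3 stays mild and level 4 stays without a grade. The rule cures the first result but not the other two.

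Lastly, check what depends on the grade. The severe wording meets neither of the other two, so level 5 is unambiguous. Serious events and the 24-hour report are defined without reference to the grade. In Section 17.0, the response to depression or anxiety is triggered by normative values of the PROMIS measures, or by observed verbal or behavioral signs, and not by an adverse-event grade.

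**The case against.** The best case on the other side has three parts.

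*The scale has a natural reading.* Mild, moderate and severe are ascending labels on one axis, and a sensible grader would take the highest that applies. This is fair as a prediction of practice, and it means that the text shows ambiguity, not demonstrated disagreement between raters. But the protocol does not state the convention, and as shown above it leaves level 3 graded below level 2.

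*Nothing turns on the split.* No stopping rule, expedited report or comparison uses mild against moderate. Each event is reported separately, with relatedness, action taken and outcome, so the label is not the only information kept. Section 3.0 says "A formal sample size estimate and power analysis was not completed as this is a feasibility study", and Section 17.0 calls the risks minimal. All of this stands, and it limits the weight of the point.

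*It could be left to the statistical analysis plan.* Such a plan can say how recorded grades are summarised. It could not recover a consistent grade for events already recorded under overlapping definitions, and here the protocol fixes the definitions itself.

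A reader might also infer more than the documents support:

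- That safety reporting is compromised. It is not, because seriousness and the 24-hour report do not use the grade.
- That all fatigue and frustration falls in the overlap. Section 17.0 does not say how much inconvenience an episode causes, so it could take any grade.
- That the scale is inverted for everything short of substantial disruption. The limit for mild is a major impact, and the protocol never equates the two terms.
- That the overlap measures a rate of misgrading. It is a relation between definitions. The protocol gives no expected number of events from which a rate could be derived.

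**Conclusion.** The point holds as a defect in a stated rule. Every event that meets the moderate wording also meets the mild wording, and an event between a minor inconvenience and a major impact meets only the mild wording. The mild or moderate label in the adverse-event reports therefore depends on the grader.

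The size is modest and cannot be put as a number. It touches one descriptive dimension of adverse-event reporting, in a study of up to 30 people with PPA and their communication partners with no stated comparison of adverse-event rates. The conclusion rests on the ordinary meaning of minor and major, and on the absence from the protocol of any rule that resolves the overlap. A grading guide outside the protocol that supplied such a rule would lessen the practical effect, but the protocol text would still need to match it.

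**What to change.** Keep the protocol's axis, impact on the participant, and reconcile the three definitions in Section 19.0 so that they are ordered, exclusive and without gaps. One way is:

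- mild: the event causes no inconvenience;
- moderate: anything from a minor inconvenience up to, but not including, a substantial disruption;
- severe: a substantial disruption, as now.

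In the table above, this gives mild at level 1, moderate at levels 2 to 4 and severe at level 5: one grade each, in order. It also drops the term major impact, so its relation to substantial disruption no longer matters. Other wordings would serve as well. If the sponsor prefers a rule to assign the highest grade that applies, the range between minor inconvenience and substantial disruption must still be closed.

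The cost is a rewording of the grading sentence, carried into whatever record is used for adverse-event reports. No data collection is added.

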## **20.0** Long-term Data and Specimen Storage and Sharing:

Data collected from this study will be stored for at least the minimum requirement of three-years after study completion. Per Northwestern's policy on Research Data: Ownership, Retention, and Access, research data from this study may be kept for as long as may be necessary to protect any intellectual property resulting from the work. Data will be stored in locked files in our research offices as well as on FSMresfiles.

# 21.0 Qualifications of Research Team to Conduct the Research:

All study team members are CITI trained.

Speech-Language Pathologists (SLPs): SLPs have completed a two-year Master's program in Speech-Language Pathology and hold a current Certificate of Clinical Competence (CCC) issued by the American Speech-Language-Hearing Association (ASHA).

Social Workers: Social workers must have completed a Master's program in Social Work and must be a Licensed Clinical Social Worker (LCSW) or Licensed Social Worker (LSW) in the State of Illinois.

Research Staff: All staff members go through a rigorous training protocol before performing study visits. This includes observing others team members perform data collection, studying the protocol and standards of procedures, and being observed by senior team members until approved to work solo.

## **Appendix**

This appendix contains a comprehensive list of all measures that may be used throughout the duration of the study. The battery may be reduced at any timepoint based on the study team judgment of participant burden and ability.

## Neuropsychological Measures

- 1. Western Aphasia Battery
- 2. Rivermead Behavioral Memory Test Version A
- 3. Mini-Mental Status Exam
- 4. Psycholinguistic Assessment of Language Processing in Aphasia reading subtest
- 5. Screen for Dysarthria and Apraxia of Speech increasing word length subtest
- 6. Boston Naming Test
- 7. Peabody Picture Vocabulary Test
- 8. Discourse Elicitation Tasks
- 9. Clinical Dementia Rating

### Questionnaires for Participant

- 1. Communication Confidence Rating Scale for Aphasia
- 2. Communication Participation Item Bank
- 3. Assessment for Living with PPA (reviewed with SLP)
- 4. PROMIS Depression computer adaptive test
- 5. PROMIS Anxiety computer adaptive test

### Questionnaires for Communication Partner

- 1. Neuropsychiatric Inventory Questionnaire
- 2. Montgomery Burden Interview
- 3. Health Utility Index
- 4. Revised Dyadic Adjustment Scale
- 5. Parent Adult-Child Relationship Questionnaire (Mother/Father)
- 6. Activities of Daily Living Questionnaire
- 7. Perception of Communication Index Dementia of the Alzheimer's Type
- 8. Communication Effectiveness Index

- 9. PROMIS Depression computer adaptive test
- 10. PROMIS Anxiety computer adaptive test

### SLP Measures

- 1. Assessment for Living with PPA
- 2. Social Network Inventory revised questionnaire
- 3. Progressive Aphasia Severity Scale
